14.4 Notifying the Research Ethics Committee

Adverse Events that do not require expedited reporting to the REC will be reported annually to the REC. This will commence annually from the date of REC favourable ethical opinion for the trial.

14.5 Follow-Up of Serious Adverse Events

All adverse events must be followed up until resolution. The site PI(s) or other delegated investigator(s) must provide follow-up adverse events report(s) if the adverse event(s) has not been resolved at the time of the initial report submission.

15. Trial Closure

15.1 End of Trial

The end of the trial will be when the last patient has completed their 6-month follow-up, at which point the 'Declaration of end of trial' form will be submitted to the REC by the ICNARC CTU.

15.2 Archiving

At the end of the trial, the ICNARC CTU will securely archive all centrally held trial-related documents for a minimum of five years, in accordance with ICH-GCP guidelines. Arrangements for confidential destruction of all documents will then be made. The site PIs will be responsible for archiving all trial-related documents (including CRFs and other essential documents) held at the participating site for a minimum of five years after the end of the study. Essential documents are those which enable both the conduct of the study and the quality of the data produced to be evaluated and to show whether the site complied with the principles of ICH-GCP and other applicable regulatory requirements.

Guidance on archiving will be provided to sites in the study-specific SOP. All archived documents, held centrally and locally, should be available for inspection by appropriate authorities upon request.

15.3 Early Discontinuation

A single interim analysis will be performed after randomisation and 30-day follow up of 50% of the target sample size. At this analysis, the composite primary endpoint will be compared between arms and the trial will be stopped early for safety if a significant difference is seen between arms (in either direction), using a

Peto-Haybittle stopping rule of p<0.001. The co-primary outcome related to predicted energy requirements will not be evaluated at the interim analysis.

Further interim analyses will be performed if requested by the Data Monitoring and Ethics Committee (DMEC).

16. Statistics and Data Analysis

16.1 Sample Size Calculation

For the composite outcome, a non-inferiority margin of an upper limit for the odds ratio of 1.2 was selected (corresponding to a 0.8% absolute increase in mortality and a 12-hour difference in median duration of ventilation). In a survey of UK PICU clinicians this margin was preferred because it would have a meaningful impact on duration of PICU admission and it is a change that would be highly relevant to patients/families. To have 90% power to detect non-inferiority, based on the upper limit of a two-sided 95% confidence interval excluding this margin, and using an outcome distribution estimated from the SANDWICH trial (4.2% mortality and log-normal distribution for duration of ventilation with median 2.9 days and lower quartile 1.0 days) requires a total evaluable sample size of 4000. To retain power for a perprotocol analysis we have allowed for cross-over of 10% and withdrawal of 5%, to set a total target size of 4700.

The percentage of the child's predicted energy requirements achieved by 72 hours after randomisation is anticipated to be approximately normally distributed, with standard deviations within each arm between 20 and 40% (22). The planned sample size in the intention-to-treat population will therefore provide >90% power (at P<0.05, two-sided) to detect a 4% absolute difference in energy intake based on the most conservative assumption of a standard deviation of 40%.

16.2 Internal Pilot Phase

Detailed in section 9.2.

16.3 Clinical effectiveness analysis methods

16.3.1 General principles

All analyses will be outlined in a statistical analysis plan (SAP) approved by an independent trial steering committee and seen by the independent data monitoring committee.

The following analysis populations will be defined:

- Per protocol (PP), which will exclude patients where consent to data collection has been withheld or withdrawn before day 30, and also patients classed as non-compliant as defined previously for the pilot evaluation stage.
- Intention to treat (ITT), which excludes patients where consent to data collection has been withheld or withdrawn for all data processing.
- ITT (energy intake), which excludes patients where consent to data collection has been withheld before 72 hours or withdrawn for all data processing.

16.3.2 Analysis of co-primary clinical outcomes

The composite outcome will be analysed using a proportional odds logistic regression model, with death during the first 30 days following randomisation ranked as the worst possible outcome (assigned value -1), and surviving patients assigned values according to their total calendar days free from mechanical ventilation during the first 30 calendar days following randomisation (with the day of randomisation counted as day 1). The model will be adjusted for important baseline variables including all variables used as stratification variables at randomisation. Baseline factors for inclusion in adjusted analyses will be selected a priori based on an established relationship with outcome for critically ill children, and not because of observed imbalance, significance in univariable analyses or by a stepwise selection method. The proportional odds assumption will be tested using Brant's test; however, it is noted that in the event that the proportional odds assumption is violated, the odds ratio retains an equivalent interpretation to alternative effect estimates using non-parametric, rank-based methods. The primary effect estimate will be the adjusted odds ratio, which will be calculated in both the PP and ITT populations with two-sided 95% confidence intervals. If the upper limit of the confidence interval is not more than 1.2 in both the PP and ITT populations, we will declare the intervention is non-inferior with respect to mortality and days free of ventilation by 30 days. Secondary analyses will test the same outcome for superiority/inferiority. The two separate components of the composite primary outcome will also be reported by arm.

Percentage of energy requirements met will be calculated in the ITT population, and for each patient is defined as the total calories consumed during the first 72 hours divided by the target calorie intake for the first 72 hours (capped at 100%). The primary effect estimate will be the difference in mean percentage of target achieved between the arms, which will be tested for superiority (at P<0.05) using a linear regression model adjusted for the same baseline variables as the analysis of the composite primary outcome. The primary effect estimate will be the difference in means, which will be reported with a two-sided 95% confidence interval.

Both co-primary outcomes will be reported in a limited number of clinically relevant subgroups, which will include patients classified by age (≤44 weeks vs >44 weeks gestational age) and reason for admission (cardiac, respiratory and other). An interaction term between subgroup and treatment arm will be added to the regression models.

A single interim analysis will be performed after randomisation and 30-day follow up of 50% of the target sample size. At this analysis, the composite primary endpoint will be compared between arms and the trial will be stopped early for safety if a significant difference is seen between arms (in either direction), using a Peto-Haybittle stopping rule of p<0.001. The co-primary outcome related to predicted energy requirements will not be tested at the interim analysis as evidence on energy intake alone will not be sufficient to change clinical practice.

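### Meeting the common odds ratio limit of 1.2 does not show non-inferiority on mortality, because the stated +0.8-point equivalent holds only under proportional odds

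*Protocol*

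**What the plan says.** Section 16.1 states that "a non-inferiority margin of an upper limit for the odds ratio of 1.2 was selected", and gives its clinical meaning as "corresponding to a 0.8% absolute increase in mortality and a 12-hour difference in median duration of ventilation". The sample size of 4,000 evaluable patients rests on "4.2% mortality and log-normal distribution for duration of ventilation with median 2.9 days and lower quartile 1.0 days".

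Section 16.3.2 ranks death by day 30 below every count of ventilator-free days and fits a proportional odds model. If the upper 95% confidence limit of the adjusted odds ratio is at or below 1.2 in both the per-protocol and the intention-to-treat populations, then "we will declare the intervention is non-inferior with respect to mortality and days free of ventilation by 30 days". Brant's test is planned, but the odds ratio is kept whatever it shows, on the ground that "in the event that the proportional odds assumption is violated, the odds ratio retains an equivalent interpretation to alternative effect estimates".

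On mortality itself, 16.3.2 reports the two components by arm, and 16.3.3 compares 30-day and 6-month mortality by adjusted logistic regression in both populations. Neither carries a margin or conditions the declaration. The interim rule in 15.3 and 16.3.2 compares the composite only.

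**The concern.** The declaration names mortality, and 16.1 lets the reader take the limit as holding excess mortality to 0.8 points. The test contains no mortality limit. Under proportional odds one odds ratio applies at every cut of the scale, including the cut between death and survival, so a limit on the common odds ratio is also a limit on mortality. If the effect on death differs from the effect on ventilation, the common odds ratio becomes an average over the ranking, and a component with 4.2% of patients has little weight in it.

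The defence in 16.3.2 is correct as far as it goes: under non-proportional odds the estimate still summarises the ranks. But that summary no longer carries the mortality equivalent by which 16.1 explains the margin. At stake is a prespecified primary conclusion about mortality in children that could stand beside a significant excess of deaths in the same report.

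**Working it through.** **Inputs.** From 16.1: control mortality 4.2%; log-normal ventilation time with median 2.9 and lower quartile 1.0 days; limit 1.2; two-sided 95% interval; 90% power; 4,000 evaluable. From 11.2: 1:1 allocation. Assumed: mortality in the intervention arm, and survivors' ventilation identical in both arms unless stated.

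**Reproducing the plan's figures.**
- Log SD = (ln 2.9 − ln 1.0)/0.6745 = 1.58. Death plus whole-day categories give 1 − Σp³ = 0.981.
- N = 12(1.960 + 1.282)² / [(ln 1.2)² × 0.981] = 126.1/0.0326 ≈ 3,867.
- At N = 4,000, SE of the log odds ratio = √[12/(4,000 × 0.981)] = 0.0553. Power = Φ(0.1823/0.0553 − 1.96) = 90.9%. The stated 4,000 is a rounded-up figure and is confirmed.
- Mortality equivalent: odds 0.042/0.958 × 1.2 = 0.0526, a risk of 5.0%, or +0.8 points. This is right under proportional odds.

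**Harm in mortality only.** If survivors are alike in the two arms, the chance that an intervention patient ranks worse than a control patient, minus the reverse, is p₁ − p₀. For small effects the common log odds ratio is then about 3(p₁ − p₀)/0.981. Fitting the model to expected counts gives the same values.
- 6.0% v 4.2%: 3 × 0.018/0.981 = 0.055, odds ratio 1.057, 95% CI 0.948 to 1.178. The limit is met. Mortality odds ratio 1.46 (1.09 to 1.94), p = 0.010; risk difference +1.8 points (0.4 to 3.2).
- 6.6% v 4.2%: 3 × 0.024/0.981 = 0.073, odds ratio 1.076, upper limit 1.199. The limit is met. Mortality z = 0.024/√[(0.042 × 0.958 + 0.066 × 0.934)/2,000] = 3.4.
- Highest observed mortality that still passes: (0.1823 − 1.96 × 0.0553) × 0.981/3 = 2.4 points, or 6.62%. Mortality is significantly worse from 5.54%. The overlap is therefore about 5.5% to 6.6% (5.43% to 6.89% with all 4,700).
- The true common odds ratio reaches 1.2 only at 0.1823 × 0.981/3 = +6.0 points, or about 10.2% mortality.

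**Simulation** (3,000 trials per row, 2,000 per arm, unadjusted, one population, control mortality 4.2%):

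| True intervention arm | Declared | Mortality significantly worse | Both |
|---|---|---|---|
| 5.0%, ventilation equal | 81% | 23% | 16% |
| 6.0%, ventilation equal | 64% | 73% | 43% |
| 6.5%, ventilation equal | 52% | 90% | 43% |
| Proportional odds, OR 1.0 | 91% | 2% | 1.5% |
| Proportional odds, OR 1.1 | 36% | 9% | 1.2% |
| Proportional odds, OR 1.2 (mortality 5.0%) | 3% | 22% | 0.1% |

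A separate run of 1,500 trials per scenario gave 41% for both at 6.0%, 42% at 6.6%, and at most about 2% under proportional odds. The first and last rows have the same mortality, exactly at the stated +0.8 points. The rule passes in 81% of trials if the harm is in death alone and in 3% if the odds are proportional. If survivors' ventilation also improved, the overlap would be larger: 63% at 6.0% with ventilation 5% shorter, and 87% at 6.5% with ventilation 10% shorter. These last two cases are illustrations.

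**Can the trial support a 0.8-point mortality limit?** With equal mortality of 4.2% and 2,000 per arm, the half-width of the 95% CI for the difference is 1.96√(2 × 0.042 × 0.958/2,000) = 1.24 points, already wider than 0.8. A test of that limit with 90% power needs (1.960 + 1.282)² × 2 × 0.042 × 0.958/0.008² ≈ 13,200 per arm.

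**The case against.** **The sentence may only name the composite.** Sections 8.2 and 8.3.1 define a single composite of survival and ventilator-free days, and the sentence in 16.3.2 lists its two parts. That reading is possible and probably what was meant. The wording nevertheless names mortality, and 16.1 supplies a mortality figure for the same limit, so a reader can fairly take it as a claim about deaths.

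**The 0.8% is a correct conversion.** A sample-size section normally gives the clinical equivalent under its own model, and Brant's test shows the assumption was in view. This stands. What is missing is the condition, and its consequence for the conclusion.

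**Mortality would be visible.** A reader might infer that the plan could hide an excess of deaths. The documents do not support that: the components are reported by arm, mortality is compared in both populations, and the monitoring committee reviews patient safety (19.4.3). The gap is only that a declaration naming mortality does not depend on any of this.

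**The scenarios are assumed.** A reader might also infer that a conflict is likely. Nothing in the protocol points to 6.0% or 6.6% mortality with unchanged ventilation, and under proportional odds the conflict is rare. Adjustment and the requirement that both populations pass would lower the joint probabilities somewhat, but both populations are judged on the same statistic, so no mortality limit is added.

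**A veto is not the obvious answer.** Blocking the declaration when mortality is significantly worse is a debatable design choice, since a result can be statistically worse and still lie within a margin. It would not restore the 0.8-point limit either: at 2,000 per arm, an observed 5.4% against 4.2% (+1.2 points) is not significant and would pass.

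**Conclusion.** The point holds as a mismatch between the conclusion and its test. An upper limit of 1.2 on the common odds ratio supports non-inferiority on the ranked composite. It bounds excess mortality at 0.8 points only if the odds are proportional, and 16.3.2 keeps the declaration when they are not. On the planning inputs, the range in which mortality is significantly worse and the composite still passes is about 5.5% to 6.6% observed against 4.2%. The 41% to 43% joint frequency depends on an assumed true mortality of 6.0% to 6.6%, unchanged ventilation in survivors, an unadjusted model and a single population. It shows what the rule permits and does not predict the result.

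The sample size, the primary model and the arithmetic behind 0.8% are sound. This should be fixed, but it is a correction of wording and presentation and does not undermine the design.

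**What to change.** - **16.3.2:** restrict the declaration to non-inferiority on the ranked composite of survival and ventilator-free days, and remove the stand-alone claim on mortality.
- **16.3.2:** present the adjusted 30-day mortality difference with its 95% CI beside the composite odds ratio as part of the primary result, and state that the conclusion is to be qualified if that interval shows harm.
- **16.1:** state that the mortality and ventilation equivalents of 1.2 apply only under proportional odds.
- **Optional:** a formal veto when the mortality interval lies wholly on the side of harm. It would be triggered in about 2.5% of trials when mortality is truly equal. If adopted, the text should say that it does not bound mortality at 0.8 points.

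The cost is an amendment of wording, carried into the SAP. No extra data or patients are needed, and the primary model does not change. A powered mortality limit of 0.8 points is not proposed, as it would need about 13,200 per arm.

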14.3 Recording and Reporting Procedures

The key safety outcomes in the GASTRIC-PICU trial are ventilator-associated pneumonia (VAP) and necrotising enterocolitis (NEC). Incidence of these events will be captured via the Case Report Forms and does not need to be reported additionally as SAEs.

Considering that all children eligible for the GASTRIC-PICU trial are critically ill and, due to the complexity of their condition, are at an increased risk of experiencing AEs – occurrences of SAEs will only be reported if they are considered to be possibly, probably or definitely causally related to the study (i.e., either as a consequence of measuring GRV, or not measuring GRV). Non-serious adverse events do not require reporting for trial purposes.

The reporting period is from the time of randomisation until 30 days post-randomisation or until final discharge from critical care unit (whichever is sooner).

All reportable SAEs (i.e., serious events which are considered possible, probably, or definitely related to the study) must be reported to ICNARC CTU within 24 hours of the site research team becoming aware of the event. Related events must be assessed for expectedness (against the list in Appendix 3). Staff should not wait until all information about the event is available before sending SAE notification. Information not available at the time of the initial report must be documented and submitted as it becomes available.

SAEs must be recorded in the patients' medical notes and reported to the ICNARC CTU using the GASTRIC-PICU SAE Reporting eCRF. If the eCRF is unavailable, the SAE report can be sent by email to [contact].

The process for recording and reporting adverse events and serious adverse events is summarised in Figure 1 (Adverse Event Reporting).

Figure 1. Adverse Event Reporting

*If there is any uncertainty about whether the SAE is associated with trial treatment, then it should be reported.

On receipt of an SAE report, a member of the ICNARC CTU will first evaluate the report for completeness and consistency. Then, a clinical member of the GASTRIC-PICU Trial Management Group (TMG) will evaluate the event to determine whether it requires expedited reporting to the Research Ethics Committee (REC). If the event is a related and unexpected SAE, the ICNARC CTU will submit a report to the REC within 15 calendar days.

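### The only pre-specified interim safety rule tests the ranked composite alone, which is insensitive to a harm confined to mortality; a 30-day mortality guideline should be added

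*Protocol*

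**What the plan says.** Protocol 16.3.2 states: "A single interim analysis will be performed after randomisation and 30-day follow up of 50% of the target sample size". At that look, "the composite primary endpoint will be compared between arms and the trial will be stopped early for safety if a significant difference is seen", in either direction, "using a Peto-Haybittle stopping rule of p<0.001". Section 15.3 gives the same rule. Energy intake is left out of this look, and neither section gives an interim test or boundary for mortality alone.

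Under 16.3.2, death by day 30 takes the value -1, one step below a survivor with no ventilator-free days. All survivors are ranked by ventilator-free days. The two components are to be reported by arm, but no interim rule is attached to them. Mortality at 30 days is a secondary endpoint (8.3.2, 16.3.3).

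Section 14.3 names VAP and NEC as the key safety outcomes and limits SAE reporting to events judged possibly, probably or definitely related. The DMEC sees accumulating data by arm (12.4), receives safety information on terms that it sets (14.3), may request further interim analyses (15.3), and monitors patient safety and reviews the interim analysis (19.4.3).

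**The concern.** A stopping rule described as being for safety should respond to the most serious harm the trial could cause. Here the test statistic is a rank comparison in which about 96% of children are ordered by ventilator-free days. An extra death moves a child to the bottom rank. It counts no more than moving that child to the bottom of the ventilation scale, and it counts very little if the child already had few ventilator-free days.

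A substantial imbalance in deaths could therefore leave the composite well short of p<0.001. The DMEC would then hold a result that had not crossed the only written safety boundary, and would have to judge the deaths with no pre-specified guide. SAE reports may not fill the gap, because only events judged related are reported.

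**Working it through.** **Inputs.** From 16.1: "4.2% mortality and log-normal distribution for duration of ventilation with median 2.9 days and lower quartile 1.0 days"; "a non-inferiority margin of an upper limit for the odds ratio of 1.2 was selected"; "requires a total evaluable sample size of 4000"; and "allowed for cross-over of 10% and withdrawal of 5%, to set a total target size of 4700". Allocation is 1:1 (11.2). Half of 4,700 is 2,350 (1,175 per arm). If the interim falls at half of the evaluable 4,000, it is 2,000 (1,000 per arm).

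**1. Reproduce the plan's own figure.** The log-SD of ventilation is ln(2.9/1.0)/0.6745 = 1.579. Cutting this into calendar days, with 4.2% deaths as the worst category, gives a sum of cubed category probabilities of about 0.019. Whitehead's proportional-odds formula then gives

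N = 12(1.960 + 1.282)² / [(ln 1.2)² × (1 − 0.019)] ≈ 3,867.

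Other day-counting rules give 3,842 to 3,939, all within 4% of the stated 4,000. Power at 4,000 is 90.4% to 91.1%. An odds ratio of 1.2 moves mortality from 4.2% to 5.0%, as stated. The outcome model used below is therefore the protocol's own.

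**2. Composite rule: deaths doubled, survivors' ventilation unchanged.** The probability that a child in the worse arm ranks worse than a child in the other arm (ties counted as half) is 0.5 + (0.084 − 0.042)/2 = 0.521. At 1,175 per arm:

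- Standard error = √[(1 − 0.019)/12 × 2/1,175] = 0.0118.
- Expected z = 0.021/0.0118 = 1.78, against a critical value of 3.29.
- Crossing probability ≈ Φ(1.78 − 3.29) = 6.5%. Simulation of 10,000 unadjusted proportional-odds fits gave 6.4%.
- At 2,000 children, expected z = 1.64 and the crossing probability is 4.9%. At 2,350 less 5% withdrawal it is 5.9%.

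The fitted common odds ratio in this scenario is only about 1.14.

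**3. Same level applied to mortality.** About 99 v 49 deaths would be expected at 1,175 per arm.

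- Standard error = √(2 × 0.063 × 0.937/1,175) = 0.01002.
- Expected z = 0.042/0.01002 = 4.19.
- Crossing probability ≈ Φ(4.19 − 3.29) = 82%. At 2,000 children it is 72%.

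**4. Other mortality levels at 2,350, survivors unchanged.** At 7.5% v 4.2%, the composite crosses 2.9% of the time and a mortality test 55%. Mortality must reach about 14%, 3.3 times control, before the composite rule has 80% power.

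**5. Sensitivity to the form of the harm (mortality doubled, 2,350 children).**

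| What else happens | Composite crosses |
|---|---|
| Extra deaths all among the longest-ventilated children | 0.1% |
| Survivors' ventilation unchanged | 6.5% |
| Survivors' ventilation worse by OR 1.05 | 18% |
| Survivors' ventilation worse by OR 1.1 | 36% |
| Survivors' ventilation worse by OR 1.2 | 76% |
| Whole scale shifts at OR 2.09 | about 100% |

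**The case against.** The low crossing rate needs a harm that acts on deaths alone. The background section describes pulmonary aspiration as the risk that GRV measurement is meant to mitigate, and aspiration or pneumonia could well lengthen ventilation too. The composite is then much more responsive, as step 5 shows. This stands, and the figure should never be quoted without its condition.

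A reader might infer that a large excess of deaths would go unnoticed, or that the DMEC would have to break the protocol to act. The documents do not support that. Sections 12.4, 14.3, 15.3 and 19.4.3 give the DMEC data by arm, control over the safety information it receives, the power to request further analyses, and a remit for patient safety. What they do not give it is a mortality threshold.

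A mortality guideline may sit in a SAP or a DMEC charter that is not shown, and a Peto-Haybittle rule on a primary endpoint that ranks death worst is a conventional choice. Both points are fair. The point here is that the protocol itself states which endpoint drives the safety stop, and that this choice performs poorly for one important kind of harm.

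A reader might also infer that VAP and NEC, as the named key safety outcomes, need the same formal boundary. No figures support one. VAP is defined by antibiotic prescribing (8.3.3) in an unblinded trial, and the signs of NEC include larger gastric aspirates, which are routinely looked for in one arm only. A boundary could respond to differences in ascertainment.

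**Conclusion.** The concern holds in a limited form. The sole pre-specified safety boundary is insensitive to a harm confined to mortality: about 5% to 6.5% crossing for a doubling of deaths, against 72% to 82% for the same threshold on mortality.

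This rests on the outcome distribution in 16.1, on unchanged ventilation among survivors, and on an unadjusted analysis; covariate adjustment would shift the figures somewhat. It does not follow that any doubling of deaths would be missed, since parallel worsening of ventilation raises the crossing rate sharply. It is a weakness of the formal rule, softened but not removed by the DMEC's discretion.

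**What to change.** In 15.3 and 16.3.2, add 30-day mortality by arm to the interim analysis, with a Peto-Haybittle p<0.001 guideline for harm, worded as a guide to the DMEC. Keep the composite rule as it stands. State that VAP and NEC will be shown to the DMEC by arm descriptively, without a formal boundary.

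The cost is a few lines of text and one extra test on data already collected at day 30 (13.1). The chance of a false harm signal is under 0.1%. Stopping for harm can only remove opportunities to declare non-inferiority, so it does not inflate that error. The sample size and final analysis are unchanged.
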